## **4.2 Total Number of Subjects and Sites**

We estimate that 100 subjects will be recruited for this study. Penn will be the only study site.

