## **6 Statistical Plan**

### **6.1 Sample Size and Power Determination**

The subjects will be recruited prospectively based on the eligibility criteria for this study. The investigators anticipate that 100 subjects will be recruited for this study between January 2020 and January 2021. This sample size is determined based on the previously noted caseload for our practice and the fact that this study duration will be limited to one year only. No comparison or control group will be used for this study. The calculation of statistical power will not be required. Patel et al showed that a rate of rise in pCO2 was 0.15 kPa/min with Hi-VNI oxygenation while measuring end tidal CO2 transcutaneously, which translates into 1.125 mmHg/min. Another study by Gustaffson et al cited average apnea duration during elective

laryngeal surgery of  $22.5 \pm 4.5$  min. Based on these values of the rate of rise for pCO2 and the average apnea duration for elective laryngeal surgery, assuming normal data distribution, the range of TcpCO2 change for procedure length within one standard deviation of the mean value (22.5 min) will be [20.25; 30.38].

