Using a normal end-tidal CO2 value of 37.5 mmHg and adding this value to the limits of the range of change in TcpCO2 listed above will give us a range of the values for TcpCO2 at the end of the procedure assuming the average duration of the procedure is  $22.5 \pm 4.5$  min. This range of the TcpCO2 at the end of the procedure would be [57.75; 67.88]. Our cutoff of TcpCO2 minus the baseline gradient between TcpCO2 and end-tidal CO2  $> 55$  mmHg is when the mode of oxygenation will be changed from Hi-VNI to an alternate method (endotracheal intubation or HFJV). The baseline gradient will be measured as the TcpCO2 minus the end-tidal CO2 during routine pre-oxygenation with a facemask. Based on the normal distribution assumption, one can deduce that only procedures with the duration one standard deviation away from the mean duration value of 22.5 min will not reach this level of TcpCO2. In other words, approximately 16% of patients will not require alternate means of ventilation (population which falls to the left of the line through a value of (22.5-4.5) on the normal distribution curve or 15.85%). Based on the author's prior experience and operative volume, there are 2-3 elective cases per week performed by the PIs that may qualify based on the inclusion/exclusion criteria to be included in the study. If 3 cases per week is used will equal to 144 qualified cases per year. For the confidence interval of 95% and the margin of error of 5% with the rate of 16%, the calculated sample size will equal to 86 individuals who might have a good chance of having their procedure completed with Hi-VNI without a need to switch to alternate mode of oxygenation. To account for the fact that some patients may not consent to be in the study or may require alternate means of oxygenation after Hi-VNI is used for other reasons, we added 14 patients to the sample size. This would lead to an estimated sample size of 100 individuals.

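### The size of 100 uses only the top of the plan's caseload range and an unstated finite-population correction: it is out of reach at 2 cases per week, and its precision is about 7 to 8 points, not 5

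*Combined protocol and SAP*

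**What the plan says.** Section 6.1 sets the number and the window: "The investigators anticipate that 100 subjects will be recruited for this study between January 2020 and January 2021". It gives the basis as practice volume, "This sample size is determined based on the previously noted caseload for our practice", together with the fact that "this study duration will be limited to one year only". Section 4.2 repeats the number, "We estimate that 100 subjects will be recruited for this study", and adds that "Penn will be the only study site".

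The supply is stated later in 6.1: "there are 2-3 elective cases per week performed by the PIs that may qualify based on the inclusion/exclusion criteria". The next step takes the upper figure alone: "If 3 cases per week is used will equal to 144 qualified cases per year". The precision inputs follow, "For the confidence interval of 95% and the margin of error of 5% with the rate of 16" per cent, and lead to a stated 86. Fourteen more are added for patients who decline or who need another mode of oxygenation for other reasons, giving 100.

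Section 6.1 also says that no power calculation is needed. It does not mention a finite-population correction, does not work out 2 cases per week, gives no consent rate, and has no plan for a shortfall.

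**The concern.** There are two linked problems. First, the stated number may exceed what the site can supply in the fixed year, because only the favourable end of the caseload range was worked through. Second, the same caseload figure appears to enter the precision formula, so that the required size falls when fewer patients are available.

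The primary endpoint in 3.4.1 is the completion rate with Hi-VNI alone, estimated in a single arm. With no power calculation, the 5-point margin is the only statistical support for the size. If that margin depends on an unstated assumption that does not fit the objectives, readers will expect a tighter estimate than the study can give.

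**Working it through.** **Inputs, all from 6.1.** Caseload 2 to 3 per week; 144 cases per year at 3 per week, so 144 / 3 = 48 weeks; target 100 in one year; expected rate p = 0.16; margin d = 0.05; 95% confidence, z = 1.96; stated size 86, plus 14.

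**Reproducing the 86.**

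- The usual precision formula, n0 = z² p(1 − p) / d², gives 1.96² × 0.16 × 0.84 / 0.05² = 206.5, or 207. This is not 86.
- The finite-population form, n = n0 / (1 + (n0 − 1)/N), at N = 144 gives 206.5 / (1 + 205.5/144) = 85.08, rounded up to 86. Adding 14 gives 100, which matches the plan. The close variant n0 / (1 + n0/N) gives 84.8, or 85.
- The same formula gives 76.1, or 77, at N = 120 and 65.8, or 66, at N = 96. With the added 14 these become 91 and 80.

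The 86 therefore rests on N = 144, the top of the range. Without the correction, a 5-point margin needs 207 patients, more than the 144 cases available.

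**Can the year supply 100?** Uptake needed = 100 / (cases per week × 48). The last column assumes 86% uptake, which is one reading of the plan's own allowance (86 / 100).

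| Cases per week | Cases in 48 weeks | Uptake needed for 100 | Enrolled at 86% uptake |
|---|---|---|---|
| 2 | 96 | 104% | 83 |
| 2.5 | 120 | 83% | 103 |
| 3 | 144 | 69% | 124 |

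With full uptake, 100 needs 100 / 48 = 2.08 cases per week. At 86% uptake it needs 2.08 / 0.86 = 2.42. As a sensitivity check, 52 working weeks at 2 per week give 104 cases, and 100 would be 96% of them.

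These counts precede losses for which the plan gives no rate: refusal (6.1), exclusion after unsuccessful mask ventilation (3.3), and discontinuation by the investigators before or during surgery (5.4).

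**Precision without the correction.** Half-width = 1.96 × √(0.16 × 0.84 / n):

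- n = 100: 7.2 points
- n = 86: 7.7 points
- n = 83: 7.9 points
- n = 80: 8.0 points

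**Precision with the correction.** Multiplying by √((N − n)/(N − 1)) at N = 144 gives 7.75 × √(58/143) = 4.9 points at n = 86, and 7.19 × √(44/143) = 4.0 at n = 100. The correction alone brings the margin under 5.

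**Does the correction fit the aim?** It is suited to describing a closed list of 144 patients. Section 2 sets out to describe the patients, pathology and scenarios for which the technique should be chosen, and 10.2 counts benefit to future patients. That inference goes beyond one year of cases at one site.

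**The case against.** The best defence is that 100 is a forecast in a self-described pilot, worded as an estimate, and reachable over much of the stated range. That stands. A reader might infer that 100 cannot be delivered at any caseload the plan gives. The documents do not support this: 69% uptake suffices at 3 per week and 83% at 2.5, and no stated consent rate rules these out.

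A reader might also infer that the one-year stop is what costs the study its 5-point margin. The numbers do not show that. Full recruitment of 100 already gives 7.2 points once the correction is removed, and falling from 100 to 86 adds only about 0.6 (7.75 − 7.19). On the plan's own finite-population basis, a lower caseload would even reduce the required size, to 66 at 2 per week. The recruitment shortfall and the precision gap are therefore separate defects, joined only by the use of 144.

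Finally, any specific low yield depends on an uptake that the documents do not give. The 86% used here is a reading of the added 14, not a stated rate. That allowance also mixes patients who decline, and so are never recruited, with patients who enrol and then switch. The shortfall at 2 per week does not depend on uptake: on the implied 48-week year, 96 is below 100 even if everyone enrols.

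**Conclusion.** The point holds in two limited parts. The target of 100 fails at the bottom of the plan's own caseload range (96 cases on its implied 48-week year) and is feasible from about 2.4 cases per week if 86% enrol. The 5-point margin is wrong as written for the study's stated objectives: it is obtained only through an unstated finite-population correction at the top-of-range caseload. The appropriate half-width at a 16% rate is about 7 to 8 points for 80 to 100 patients, even if recruitment is full.

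This rests on the 48 weeks implied by the plan, on the plan's 16% rate taken as given, on the normal approximation the formula uses, and on reading Section 2 and 10.2 as aiming beyond the year's caseload. If the aim were only to describe that year's cases, the correction could be defended, but it would have to be stated.

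**What to change.** In 4.2 and 6.1:

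- State expected enrolment at 2, 2.5 and 3 cases per week with an explicitly assumed uptake. For example, 86% gives about 83, 103 and 124, with the last two capped at 100.
- Remove the finite-population correction and the 86 derived from it.
- Replace the 5-point margin with the 95% half-width at the expected n: about 7.9 points at 83 and 7.2 at 100.
- Present 100 as a size set by feasibility, which 6.1 already gives as its first reason, and not as one derived from a 5-point margin.

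Keeping the 5-point margin without the correction is not a practical alternative, since 207 patients exceed even the 144 cases expected at 3 per week. The change is to text only and adds no patients or time. Its cost is that the stated precision, and possibly the stated enrolment, become less favourable.

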## 2 Study Objectives

The overall objectives for this study are to establish the efficacy of Hi-VNI in upper airway surgery from the anesthesiologist's and surgeon's perspectives, and to describe the ideal patient and the ideal pathology as well as suitable clinical scenarios when this oxygenation technique should be selected. This study will not change labeling of the Hi-VNI Precision Flow device by the Vapotherm and is not intended to change marketing claims of the manufacturer pertaining to this device.

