## **6.2 Statistical Methods**

Descriptive statistics will be used to characterize the data distribution with normally distributed data presented as means and standard deviation, otherwise median and interquartile range will be used. Proportions will be presented in numbers and percentages. All data analyses will be performed using a statistical tool (SPSS, version 15.0, SPSS). Mann-Whitney U test or Student's t-test and Kruskal-Wallis or ANOVA test will be used depending on the data distribution and the number of variables. All statistical analyses will use a  $p < 0.05$  as statistically significant. Any additional statistical analyses will be determined during secondary data analysis with help from a statistician.

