## **10.2 Benefits**

The potential direct benefits to the subjects who will consent to participate in this study are a chance of shorter surgical case duration, potential avoidance of intubation, and lower risk of barotrauma and airway trauma if Hi-VNI is used without a need for intubation or HVJV use during the procedure. This study also offers indirect benefits to the society and the future patients by attempting to further evaluate the efficacy of the Hi-VNI as a primary or adjunct oxygenation technique during upper airway surgery. This study will not change labeling of the Hi-VNI Precision Flow device by the Vapotherm and is not intended to change marketing claims of the manufacturer.

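### At the plan's 16% rate, a ±5-point margin for future patients needs 207 subjects, not 86; the design gives about ±7.7 points with 86 treated and ±7.2 with 100

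*Combined protocol and SAP*

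**What the plan says.** The primary endpoint (3.4.1) is the proportion of cases completed with Hi-VNI as the only means of oxygenation. Section 6.1 takes 16% as the expected value of that proportion. It gives the caseload as "there are 2-3 elective cases per week performed by the PIs that may qualify", continues with "If 3 cases per week is used will equal to 144 qualified cases per year", and then states that for a 95% confidence interval and "the margin of error of 5% with the rate of 16%, the calculated sample size will equal to 86 individuals". It describes these 86 as people with a good chance of finishing on Hi-VNI alone. To cover non-consent and switches for other reasons, "we added 14 patients to the sample size", which gives 100. No formula is shown and no finite-population correction is mentioned.

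The opening of 6.1 gives a different basis for the same 100: "This sample size is determined based on the previously noted caseload for our practice", together with the one-year limit on the study.

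On the target of inference, section 2 wants to describe "suitable clinical scenarios when this oxygenation technique should be selected", and 10.2 says "This study also offers indirect benefits to the society and the future patients". On reporting, 6.2 says "Proportions will be presented in numbers and percentages", and 6.3.2 plans averages and standard deviations for the primary outcome. Neither section plans a confidence interval for the completion rate.

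**The concern.** A 95% interval of ±5 points around a proportion of 16% ordinarily needs more than 200 subjects, so 86 is far too small unless something has reduced it. The caseload of 144 in the preceding sentence points to a finite-population correction. That correction is legitimate when the aim is to describe a fixed, fully listed population from which a sample is drawn. It is not legitimate when the patients of one year stand for those who come later.

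This is the only statement of precision for the primary endpoint, and 6.1 builds its total of 100 on it. A reader would take ±5 points as what the study can say about completion rates in general. No interval is planned in the analysis, so the report itself would not correct that impression.

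**Working it through.** **Inputs, all from 6.1:** rate p = 0.16; margin d = 0.05; 95% confidence, so z = 1.96 (two-sided, assumed because the text speaks of a confidence interval and margin of error); yearly caseload N = 144; planned total 100.

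**1. Standard formula.** n0 = z²p(1−p)/d² = 1.96² × 0.16 × 0.84 / 0.05² = 206.5, so 207.

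**2. Reproducing the plan's 86.** Finite-population correction: n = n0 / (1 + (n0 − 1)/N) = 206.5 / (1 + 205.5/144) = 85.1, rounded up to 86. The uncorrected variants tried do not give 86:

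| Variant, no correction | n |
|---|---|
| 90% two-sided, or 95% one-sided | 146 |
| 95% with continuity correction | about 227 |
| 5 points as total width | 827 |
| rate of 50% | 385 |

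So 86 is not an arithmetic slip. It is the corrected size for a population of 144.

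**3. What the correction implies.** With n = 86 and N = 144 the corrected half-width is 1.96 × √(0.16 × 0.84/86 × (144 − 86)/143) = 4.93 points. That is within ±5, but only as a statement about those 144 cases.

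**4. The size follows the caseload, not the precision wanted.** The 144 is 3 × 48 weeks. At the lower end of the plan's caseload range, 2 × 48 = 96 cases, the same formula gives 206.5 / (1 + 205.5/96) = 65.8, so 66 for the same ±5. The planned 100 would then exceed the whole population. A smaller practice does not need fewer patients to learn equally precisely about future ones.

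**5. Half-width without the correction,** 1.96 × √(p(1−p)/n), in percentage points:

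| Rate | n = 86 | n = 100 |
|---|---|---|
| 6% | 5.02 | 4.65 |
| 16% | 7.75 | 7.19 |
| 50% | 10.57 | 9.80 |

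At 16% these are 7.75/5 = 1.55 and 7.19/5 = 1.44 times the stated margin.

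**6. Exact (Clopper-Pearson) 95% intervals.** 14/86: 9.2% to 25.8%. 16/100: 9.4% to 24.7%. 6/100: 2.2% to 12.6%.

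**7. Why 6% is shown.** Section 6.1 starts from 37.5 mmHg, a rise of 1.125 mmHg/min, a threshold of 55 mmHg and a duration of 22.5 ± 4.5 min. The threshold is reached at (55 − 37.5)/1.125 = 15.56 min; z = (15.56 − 22.5)/4.5 = −1.54; the lower tail is 6.1%. The plan's own inputs therefore point to about 6% rather than 16%. The 50% row is an assumption, taken as the widest case.

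**8. The meaning given to the 86.** At 16%, 0.16 × 86 = 13.8, so about 14 of the 86 would be expected to complete on Hi-VNI alone. The 86 is a denominator, not a count of likely completers.

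**The case against.** The strongest reply has four parts.

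- **The target population is a judgement.** Section 6.1 attaches no population to the ±5, and 3.1 says the study will describe selected cases at this institution. For the 144 cases in view the margin is correct. This reading is possible, but it does not fit the protocol's aims. Sections 1, 2 and 5.5 all seek to say when the technique should be selected, and 10.2 looks to future patients. If the narrow target was meant, 6.1 would have to name the correction and its population.
- **The correction is inferred.** The match uses the rate rounded to 16%; the unrounded 15.85% gives 84.8, so 85. The inference remains strong, because 144 stands in the preceding sentence. The conclusion does not depend on it: without a correction, 86 is simply wrong at 16%.
- **The 16% is itself doubtful.** At about 6%, ±5 roughly holds with 86 to 100 subjects. This stands and limits the size of the finding. It does not rescue a sentence that specifies 16%, and it is a reason to state precision across several rates.
- **The consequences are modest.** This is a single-arm pilot whose size is also justified by caseload, and no decision uses the ±5. With counts and percentages reported, a reader could compute an interval. All of this is fair, and it is why no change in enrolment is asked for. The published precision would still be wrong as written.

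A further caution also stands. The number analysed could fall below 86, because 3.3 removes patients in whom mask ventilation fails and 5.4 allows discretionary withdrawal during surgery. With 80 the half-width at 16% would be 1.96 × √(0.16 × 0.84/80) = 8.0 points.

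**Conclusion.** The concern holds. At 16%, ±5 points for patients beyond the year's caseload needs 207 subjects against the 86 stated; the design gives about ±7.7 points with 86 and ±7.2 with 100. The conclusion rests on a two-sided 95% interval, the normal approximation for planning (exact intervals at 16% are slightly wider), and a target population that extends past the 144 cases of one year. The shortfall is conditional on the 16% rate: it largely vanishes near 6% and grows towards 50%. The description of the 86 as likely completers is wrong on the plan's own rate. The total of 100 is not undermined, since it has a separate feasibility basis.

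**What to change.** In 6.1, remove the finite-population correction and the ±5 claim, and replace them with text such as:

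> With 86 to 100 treated subjects the 95% CI half-width is about 7 to 8 percentage points at a 16% completion rate (exact CI for 16/100: 9.4% to 24.7%) and about 10 points at 50%; at 6% the exact CI for 6/100 is about 2% to 13%.

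Delete the wording that presents the 86 as patients likely to complete on Hi-VNI. Keep 100 as a feasibility-based size, as the opening of 6.1 already has it. If the 16% is revised when it is reconciled with the plan's other inputs, carry the new rate into this sentence.

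In 6.3.2, add:

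> The completion rate will be reported with an exact (Clopper-Pearson) 95% CI.

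The cost is a rewording of 6.1 and one line in 6.3.2. The stated precision becomes less favourable; enrolment does not change.

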### Schedule of events:

### 3.4 Study Endpoints

#### 3.4.1 Primary Study Endpoint

The primary endpoint for this study will be case completion rate without alternative mode of oxygenation. In other words, for each case, the ability to complete the surgical procedure with use of only Hi-VNI device for oxygenation will be assessed.

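### Section 6.1 presents a total of 86 to be observed as patients likely to finish on Hi-VNI alone, and justifies the extra 14 by groups that are not losses from the 100 recruited

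*Combined protocol and SAP*

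**What the plan says.** The sample-size argument in Section 6.1 of the combined protocol and SAP runs in four steps.

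- **Rate.** From a CO2 rise rate and a distribution of apnoea durations it concludes that "approximately 16% of patients will not require alternate means of ventilation".
- **Pool.** "If 3 cases per week is used will equal to 144 qualified cases per year".
- **Calculation.** "For the confidence interval of 95% and the margin of error of 5% with the rate of 16" per cent, it states that "the calculated sample size will equal to 86 individuals who might have a good chance of having their procedure completed with Hi-VNI", without a change of mode.
- **Add-on.** Because "some patients may not consent to be in the study or may require alternate means of oxygenation after Hi-VNI is used for other reasons", it says "we added 14 patients to the sample size", which gives 100.

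Other sections fix what these numbers can mean. Section 3.4.1: "The primary endpoint for this study will be case completion rate without alternative mode of oxygenation". Section 4.2: "We estimate that 100 subjects will be recruited for this study". Section 4.5 allows enrolment only once consent has been given.

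Subjects can leave by three routes. Under Section 3.3, a patient whose mask ventilation fails at induction is excluded before Hi-VNI begins. Under Section 5.4, investigators may discontinue a subject judged a poor candidate, either just before surgery or while it is under way. Under Section 5.4.1, no further follow-up data are required from withdrawn subjects.

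**The concern.** A precision calculation for a proportion returns the number of patients to observe, successes and failures together. Section 6.1 instead describes its result as people likely to succeed, in the same paragraph that puts the chance of success at 16%.

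The reasons for the 14 have a related fault. A patient who declines is never one of the 100 recruited. A patient who switches has supplied a primary-endpoint result, namely a failure.

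Two things are at stake. First, Section 3.1 intends to describe favourable clinical scenarios from cases completed on Hi-VNI alone, and a reader of 6.1 could misjudge how many such cases there will be. Second, if switches are regarded as attrition, and Section 5.4 lets a subject be discontinued mid-procedure, failures could drop out of the denominator and the completion rate would be biased upward.

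**Working it through.** **Inputs.** All are from Section 6.1: 95% confidence (z = 1.96); margin d = 0.05; rate p = 0.16; N = 144 qualifying cases a year; add-on 14; starting CO2 37.5 mmHg; rise 1.125 mmHg/min; cutoff 55 mmHg after subtracting the baseline gradient; duration 22.5 ± 4.5 min.

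**1. Reproducing the 86.**

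- Uncorrected: n0 = z²p(1 − p)/d² = 1.96² × 0.16 × 0.84 / 0.05² = 206.5.
- With a finite-population correction: n = n0/[1 + (n0 − 1)/N] = 206.5/(1 + 205.5/144) = 85.1, rounded up to 86.

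The section does not name the correction. It is inferred, because the uncorrected formula gives 207 and does not match. On this basis 86 is the total to be observed.

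**2. Expected completions at the stated 16%.**

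- 86 × 0.16 = 13.8 completions and 72.2 switches (95% binomial range for completions 7 to 21).
- 100 × 0.16 = 16 completions and 84 switches (range 9 to 23).

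**3. Expected completions at the rate the CO2 inputs imply.**

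- Time to the cutoff: (55 − 37.5)/1.125 = 15.6 min.
- z = (15.6 − 22.5)/4.5 = −1.54, so the share of shorter procedures is 6.1%.
- 86 × 0.061 = 5.3; 100 × 0.061 = 6.1.

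Section 6.1 takes its 16% at 22.5 − 4.5 = 18 min. Its own value there is 37.5 + 18 × 1.125 = 57.75 mmHg, already above 55. The 16% and the cutoff therefore do not agree and must be reconciled.

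**4. Does 100 still meet the precision target?** Half-width at p = 0.16:

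| n | with correction (N = 144) | without correction |
|---|---|---|
| 86 | 4.9 points | 7.7 points |
| 100 | 4.0 points | 7.2 points |

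On the section's implied method, both 86 and 100 meet the 5-point margin.

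**5. Who can be lost from 100 recruited?**

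| Group | Where it falls | Loss from the 100? |
|---|---|---|
| Declines consent | Before recruitment (4.2, 4.5) | No; reduces the yield from the 144 |
| Switches mode after starting Hi-VNI | Primary-endpoint failure (3.4.1) | No; stays in the denominator |
| Mask ventilation fails at induction | Excluded before Hi-VNI (3.3) | Yes; no rate given |
| Discontinued before surgery | 5.4 | Yes; no rate given |
| Discontinued during surgery | 5.4, 5.4.1 | Unclear; needs a rule |

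**6. Illustration of the denominator risk.** Suppose all 100 start, 16 complete, and 14 of the 84 switchers are treated as attrition. The reported rate becomes 16/86 = 18.6% instead of 16/100 = 16.0%. The shift is 2.6 points, about half the target margin.

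**The case against.** The strongest reply is that this is loose wording with no effect on the design. Section 6.1 says that its sample size rests on caseload and a one-year limit, in a single-arm pilot with no power calculation. The arithmetic to 86 and then to 100 can be reproduced, and the 16% stands in the same paragraph for anyone who wants the yield. Most of this is right. The total of 100 need not change.

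Three stronger readings are tempting, and the documents do not support them.

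- **That the plan overstates its completers about six-fold** (86/13.8 = 6.25, or 86/16 = 5.4 against 100). The plan prints no expected number of completers. Its wording is hedged, so the fault lies in how the 86 is described and not in a forecast.
- **That precision for means among completers collapses** because there are about 16 of them and not 86. No such estimate is planned; Section 3.1 speaks only of describing scenarios from completed cases.
- **That switched subjects will be replaced.** No replacement rule exists. The documents leave room for removal through 5.4 but do not direct it.

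It may also be said that the add-on is confined to switches for reasons other than CO2. That is so, but Section 3.4.1 makes no exception by reason, so those switches are failures too.

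What remains is a wrong statement in the sample-size basis and an unsettled denominator.

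**Conclusion.** The point holds as an error of description and of attribution. The 86 is a total, within which about 14 completions are expected at the plan's 16% (16 if all 100 start), or about 5 to 6 at the 6.1% its CO2 inputs imply. The added 14 are assigned to two groups, neither of which is a loss from 100 recruited subjects. The groups that can be lost before Hi-VNI starts are not mentioned in 6.1.

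This does not show that 100 is too few. With the inferred finite-population correction, 100 gives a half-width of 4.0 points.

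The practical consequence is the denominator. With switches described as an allowance and discontinuation during surgery permitted, the plan does not guarantee that failures are counted.

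The conclusion rests on the inferred correction with N = 144 and on the plan's rate and CO2 figures as printed. Both rates reflect the CO2 cutoff alone, so switches for other reasons would lower the yield further.

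**What to change.** Reword the last part of Section 6.1 and add one sentence to Section 5.4. No additional enrolment is needed.

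1. State that 100 subjects are recruited and that 86, the total from the precision calculation, is the minimum number to be started on Hi-VNI. Name the finite-population correction if it was used.
2. Say that the margin of up to 14 covers only consented subjects who never start Hi-VNI (failed mask ventilation, or withdrawal or discontinuation beforehand). Mark this as an assumption, since the plan gives no rate.
3. Move non-consent to the number of patients approached out of the 144.
4. Define the primary denominator as every subject started on Hi-VNI. Any switch for any reason, including discontinuation during surgery under 5.4, counts as non-completion and is not replaced. Record the primary outcome for these subjects despite 5.4.1.
5. Print the expected completions: about 14 (86 started) to 16 (100 started) at 16%, to be revised once the 16% is reconciled with the 55 mmHg cutoff.

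The cost is the rewording and a less favourable stated yield.
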